8.3.3 Safety

Descriptive summary statistics for] adverse and serious adverse events will be reported. Adverse events will be grouped by body system and grade and will be tabulated as numbers and percentages; serious adverse events will be enumerated and described as appropriate.

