4. STUDY DESIGN

4.1 Design overview

This clinical trial is a single-center, open-label, single-arm study of 30 individuals with SSc and fatigue.

The study will allow for subjects to continue standard of care medications for the management of SSc as background therapy.

The study design consists of a single, four-week intervention. The screening and baseline visits can be combined when the screening is not able to be performed over the phone in advance.

- **Screening phase:** up to 4 weeks prior to baseline visit
- **Observation period:** During this one week phase participants will track their daily Raynaud attack frequency and duration using a diary. This will occur in the seven days preceding the baseline intervention phase.
- **Open-label intervention phase:** This consists of a four-week period during which participants will use the Apollo wearable system as needed to manage symptoms including fatigue. During the intervention phase participants may use the wearable at their discretion and control. Participants will track their daily Raynaud attack frequency and duration using a diary during week 4 of Apollo use. Participants will complete questionnaires on day 1 of the open-label and intervention phase, and at their follow-up four weeks later.

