7.1.2.1 Visit 0 – Screening

Screening evaluations will be performed only after the participant has provided written informed consent. The following evaluations will be performed and information obtained up to 28 days before the baseline visit.

- Participant information and obtaining of written informed consent
- Eligibility: Assessment of inclusion and exclusion criteria (see Section [5.1](#))
- Demographic data, including sex, race, ethnic group, year of birth, smoking history and alcohol consumption
- Medical and surgical history
- Prior and concomitant therapy
- Medication history

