7.5.1.1 Definitions**Definition of adverse event****(AE)**

In a clinical study, an AE is any untoward medical occurrence (i.e., any unfavorable and unintended sign [including abnormal laboratory findings], symptom or disease) in a patient or clinical investigation participant after providing written informed consent for participation in the study. Therefore, an AE may or may not be temporally or causally associated with the use of a medicinal (investigational) product.

A surgical procedure that was planned prior to the start of the study by any physician treating the participant should not be recorded as AE (however, the condition for which the surgery is required may be an AE).

In the following differentiation between medical history and AEs, the term “condition” may include abnormal physical examination findings, symptoms, diseases, laboratory results, and ECG findings.

- Conditions that started before signing of informed consent and for which no symptoms or treatment are present until signing of informed consent are recorded as medical history (e.g., seasonal allergy without acute complaints).
- Conditions that started before signing of informed consent and for which symptoms or treatment are present after signing of informed consent, at *unchanged intensity*, are recorded as medical history (e.g., allergic pollinosis).
- Conditions that started or deteriorated after signing of informed consent will be documented as AEs.

Definition of serious adverse event (SAE)

An SAE is classified as any untoward medical occurrence that, at any dose, meets any of the following criteria (a – f):

- a. Results in death
- b. Is life-threatening

The term ‘life-threatening’ in the definition refers to an event in which the participant was at risk of death at the time of the event, it does not refer to an event which hypothetically might have caused death if it were more severe.

- c. Requires inpatient hospitalization or prolongation of existing hospitalization

A hospitalization or prolongation of hospitalization will not be regarded as an SAE if at least one of the following exceptions is met:

- The admission results in a hospital stay of less than 12 hours
- The admission is pre-planned
(i.e., elective or scheduled surgery arranged prior to the start of the study)
- The admission is not associated with an AE
(e.g., social hospitalization for purposes of respite care).

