7.5.1.3 Assessments and documentation of adverse events

The investigator has the obligation to report AEs. All non-serious events will be assessed and recorded during the specified observational phase (from signing the informed consent form up to 30 [+5] days after last study medication intake), whether believed to be related or unrelated to the treatment. AE forms will be included. The record will include clinical symptoms or final diagnosis when available, date of appearance, duration, severity and relationship to treatment. A record will also be kept of the action taken and the follow-up until resolution of the AE.

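### Adverse events count from consent but are tabulated with no split at first device use, so the single-arm safety table mixes pre-exposure with device-period events

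*Combined protocol and SAP*

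**What the plan says.** **When counting starts.** Section 7.5.1.1 states: "Conditions that started or deteriorated after signing of informed consent will be documented as AEs". Section 7.5.1.3 sets the recording window for non-serious events as "from signing the informed consent form up to 30 [+5] days after last study medication intake". There is no study medication in this trial, so I read the end of that window as counted from last device use.

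**When consent comes.** Section 7.1.2.1 states: "Screening evaluations will be performed only after the participant has provided written informed consent". On the interval it says: "The following evaluations will be performed and information obtained up to 28 days before the baseline visit". Section 4.1 gives the same limit ("up to 4 weeks prior to baseline visit") and also allows no gap at all: "The screening and baseline visits can be combined when the screening is not able to be performed over the phone in advance".

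**When exposure starts.** Sections 4.1.2 and 7.1.2.2 hand over the device at the baseline visit.

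**When events are collected.** Sections 7.1.2.2 and 7.1.2.3 list adverse event recording at baseline and at Visit 2. No later contact is scheduled.

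**What is tabulated.** Section 8.3.3: "Adverse events will be grouped by body system and grade and will be tabulated as numbers and percentages". No section defines treatment-emergent or on-device events. The related / not related call required by section 7.5.1.2.3 is not mentioned in the planned table. The analysis set under section 8.1 is limited to participants who used the device, and it is stated for the primary endpoint and secondary outcomes. No safety set is named.

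**The concern.** Following these rules as written, a worsening of systemic sclerosis during screening or the observation week, in someone who goes on to wear the device, is an adverse event. It is picked up at the baseline visit and tabulated beside events that occurred on the device, with nothing to tell the two apart.

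Two features make this matter. Tolerability is named in the primary objective (Synopsis and section 2), and with a single arm there is no control group against which to read background events. The length of the pre-device period also differs between participants for reasons unrelated to the device: none if visits are combined, at least a week if consent precedes the observation week, up to four weeks otherwise. The reported percentages would then depend partly on appointment scheduling.

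**Working it through.** The plan states no figure for the share of events before first use, so there is nothing to reproduce. The check is a person-time calculation.

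**Inputs**
- P, days from consent to first use: 0 (combined visits, section 4.1), 7 (observation week only, section 4.1), 28 (maximum, section 7.1.2.1). I add 14 as an intermediate value.
- D, days from first use to Visit 2: 28, or 25 to 31 over the visit window in the schedule of events. The device is assumed to be used throughout.
- F, days of collection after last use: 30, or 35 with the allowance (section 7.5.1.3). F = 0 if collection in practice ends at Visit 2.
- Event rate: not given in the documents. Assumed constant per day.

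**Formula:** pre-device share = P / (P + D + F).

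| P | Stated window (D = 28, F = 30) | Collection ends at Visit 2 (D = 28, F = 0) |
|---|---|---|
| 0 | 0% | 0% |
| 7 | 7/65 = 10.8% | 7/35 = 20.0% |
| 14 | 14/72 = 19.4% | 14/42 = 33.3% |
| 28 | 28/86 = 32.6% | 28/56 = 50.0% |

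**Range for P = 28.** On the stated window, from 28/(28+31+35) = 29.8% to 28/(28+25+30) = 33.7%. To Visit 2 only, from 28/(28+31) = 47.5% to 28/(28+25) = 52.8%.

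**Sensitivity to the constant rate (P = 28, D = 28, follow-up at the background rate).** If events are twice as frequent in the device period as before it, the share is 28/(28+56+30) = 24.6% on the stated window and 28/(28+56) = 33.3% to Visit 2. If they are half as frequent, it is 28/(28+14+30) = 38.9% and 28/(28+14) = 66.7%.

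**Sensitivity to duration of use.** A participant who stops after one day and is followed for 30 more has 28/(28+1+30) = 47.5%. Sections 6.5, 8.2.2 and 8.4 refer to two weeks where the design sections say four, and these need reconciling. With 14 days of use the 28-day share would be 28/(28+14+30) = 38.9% on the stated window.

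**The case against.** The best case for leaving the text alone has several parts.

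- *The eligibility rules already filter the worst pre-device events.* Section 5.1.1 requires steady doses of several drug classes for four weeks before baseline, section 5.1.2 excludes hospitalization in the same period, and section 7.1.2.2 reconfirms eligibility at baseline. A screening-period flare that led to admission or a change in those drugs would keep the person off the device and out of the analysis set. This stands. It pushes the pre-device rate below the device-period rate, so the constant-rate shares are upper-end figures. Milder new or worsened events still enter the table.
- *The analysis set contains only device users.* That removes people who never used the device. It does not remove the earlier events of those who did.
- *Onset date and relatedness are recorded, so the split can be made at reporting.* True, and that is why the change is cheap. But recording a date does not plan a split, and in an open-label trial a choice made at reporting is made with the data in view.
- *Section 8 is a summary, and a fuller SAP is promised.* Also true. Silence in 8.3.3 should not be read as a decision to discard relatedness. Still, the counting and tabulation rules that are written do pool the events.
- *Pooling adds events to the device table and so hides nothing.* The total is not understated, but the table no longer says which events coincided with use.

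A reader might go further and infer that about half of the reported events could predate exposure. The documents do not support that as a general statement: the window in section 7.5.1.3 runs 30 days past last use, and 28 days is a limit on screening, not its usual length. For participants with four weeks of use, half requires that all of them take the full 28 days and that collection stops at Visit 2. The absence of any scheduled later contact makes the second condition possible but does not establish it.

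**Conclusion.** The structural point holds. As written, the safety table for a single-arm trial pools pre-exposure events with device-period events, and the mix depends on scheduling.

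The size is less certain. Under a constant rate and four weeks of use, the pre-device share runs from nothing to about one third on the protocol's own window, and reaches one half only if collection ends at Visit 2. The one-third ceiling is over schedules, not over event rates: it rises if events are rarer on the device than before it and falls if they are more frequent, which is the direction the eligibility criteria suggest. The documents give neither a rate nor a distribution of screening intervals, so no single expected value can be stated.

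This should be corrected before the data are summarized. It does not touch the primary efficacy analysis. Nor should the correction be oversold: without a control arm, a split by onset shows when events occurred relative to exposure and cannot establish that the device caused them.

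**What to change.** Add a paragraph to section 8.3.3 that:

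1. lists events with onset from consent to first device use separately, outside the main table;
2. makes events with onset or worsening on or after first device use the main safety table, with all participants who used the device as denominator;
3. shows the related / not related classification within that table.

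Because the post-device window decides which column of the working applies, the same paragraph should say how events after Visit 2 are collected, or end the window at Visit 2.

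The cost is one paragraph of wording. Section 7.5.1.3 already records onset date and relationship, and the system logs device use (section 6.5). The only recording detail to add is that a pre-device event that worsens after first use gets its own dated entry. No new visits or measurements are needed for the split.

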8.4 Planned interim analyses

No formal interim analysis of this short, two-week study will be performed.

8.5 Determination of sample size

SSc is a rare disease. The planned minimum sample size of 30 SSc participants is based on practical considerations to obtain preliminary estimates of the magnitude of treatment differences in efficacy and safety rather than a desired power for a pre-specified difference as would be necessary for a confirmatory study. However, with this proposed sample of 30 participants we can calculate the magnitude of treatment differences (riociguat – placebo) for the primary efficacy endpoint – the change from baseline to end of double-blind treatment in fatigue scales. There would be 80% power to detect an effect size (mean treatment difference divided by standard deviation) of While we expect that 30 subjects will be enough participants to see a significant treatment effect in this study population, we have written this protocol to allow for the inclusion of up to 100 subjects should 30 subjects be found to be an insufficient number for any reason.

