Diagnosis and main criteria for inclusion	
 ▪ Men or women aged 18 years and older, inclusive ▪ Systemic Sclerosis as defined by 2013 the American College of Rheumatology (ACR) / European League Against Rheumatism (EULAR) classification. ▪ Steady daily doses of any immunosuppressive medication, vasodilators, antidepressants and anxiolytic use for 4 weeks prior to baseline. ▪ PROMIS-fatigue score of at least 45 ▪ Currently owns and operates a smart phone regularly ▪ Ability to provide informed consent
Study Design	Open label, single-arm, single center US study
Type of control	None
Number of participants	30
Primary outcome variable	Change in the PROMIS-Fatigue scale at four weeks

30

Plan for statistical analysis

The planned sample size of 30 SSc participants is based on practical considerations to obtain estimates of the magnitude of treatment differences for efficacy and safety rather than a desired power for a pre-specified difference.

From similar studies on Rheumatoid Arthritis and Systemic Lupus Erythematosus, the improvement of T-score after treatment is about 5. The standard deviation for general population is 10. However, we are restricting our population to participants with fatigue T-scores of less than 54 (with low score indicating high fatigue). With the range of T-score reduced about half, we expect the standard deviation to be about 5. The effect size is expected to be 1 (5/5).

Using paired t-test, we have 86% power to detect the effect size of 1 when we recruit 30 patients at a significance level of 0.05. We asked the IRB for the option of increasing the number of patients to 40, which will give us about 81% power to detect a smaller effect size of 0.8 at a significance level of 0.05.

Descriptive statistics will be derived for all clinical variables, mean and standard deviation for continuous outcomes and percentages for categorical and dichotomous variables.

The primary outcome of interest is fatigue, as measured by the FACIT-Fatigue. We will compare the mean change from baseline and four weeks in a repeated measures model.

The p-values resulting from formal statistical tests will be interpreted from a hypothesis-generating, rather than a confirmatory framework.

Table of contents

1. Introduction	9
1.1 Background	9
1.1.1 Scleroderma (systemic sclerosis).....	9

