A data and safety monitoring plan will be implemented by the Principal Investigator to ensure that there are no changes in the risk/benefit ration during the course of the study and that confidentiality of research data is maintained. Each member of the study team will meet with the PI and review confidentiality issues and complete a confidentiality agreement, prior to having contact with research subjects. Investigators and study personnel will meet **every 2 months** to discuss the study (e.g. study goals and modifications of those goals; subject recruitment and retention; progress in data coding and analysis; documentation, identification of adverse events or research subject complaints; violations of confidentiality) and address any issues or concerns at that time. Minutes will be kept for these meetings and will be maintained in the study regulatory binder. Any instances of adverse events will be reported immediately to the University of Pittsburgh IRB. The IRB renewal for this study will include a summary report of the Data and Safety Monitoring Plan findings from prior renewal period.

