8.1 General considerations

This section presents a summary of the planned statistical analyses. A statistical analysis plan (SAP) will be written for the study that contains detailed descriptions of the analyses to be performed. The SAP will be finalized prior to unblinding of the data.

Continuous variables will be summarized using descriptive statistics including n, mean, median, standard deviation, range (e.g., minimum and maximum). Qualitative variables will be summarized using counts and percentages. Graphical methods will be used in this pilot study to assess the pattern of response over time for key variables and to assess the relationships among variables.

Unless otherwise specified, statistical analyses will be performed using SAS Version 9 or higher. Where appropriate, statistical tests will be conducted at the 0.05 significance level (with no adjustments for multiplicity) using two-tailed tests and p-values will be reported.

Given the rare nature of SSc and the consequent small sample size for this pilot study, the statistical power of any comparisons is limited (i.e., there is sufficient power to detect only large treatment differences). As such the analysis will be largely descriptive in nature. The p-values resulting from formal statistical tests will be interpreted from a hypothesis-generating, rather than a confirmatory framework.

Analysis sets

As this is an open-label study, all participant who have used the Apollo system wearable for at least one dose (one day) will be analyzed. The primary endpoint and all secondary outcomes will be assessed using this analysis set.

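### Section 8.5 lets the sample grow from 30 to 100 on any ground, with no bar on using outcome data, so the 0.05 level is not guaranteed; the sections also disagree on N

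*Combined protocol and SAP*

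**What the plan says.** Three sample sizes stand in the current text.

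- Section 4.1: "This clinical trial is a single-center, open-label, single-arm study of 30 individuals with SSc and fatigue". No extension is mentioned.
- Synopsis, plan for statistical analysis: 30, with an option requested from the IRB of "increasing the number of patients to 40, which will give us about 81% power to detect a smaller effect size of 0.8". This option is argued from design-stage power.
- Section 8.5: 30 as a planned minimum, then "we expect that 30 subjects will be enough participants to see a significant treatment effect in this study population", with provision to "allow for the inclusion of up to 100 subjects should 30 subjects be found to be an insufficient number for any reason".

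The surrounding rules are these.

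- Section 8.1: "statistical tests will be conducted at the 0.05 significance level (with no adjustments for multiplicity) using two-tailed tests and p-values will be reported". The p-values are to be read as hypothesis-generating.
- Section 8.4: "No formal interim analysis of this short, two-week study will be performed".
- Section 6.2: no randomisation and no blinding.
- Data Safety and Monitoring Plan: the team meets every two months on a list that includes "study goals and modifications of those goals; subject recruitment and retention; progress in data coding and analysis".

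No section names the person who decides on an increase, the timing, or the data that may be used. None says that efficacy results are withheld until enrolment closes. Section 8.1 promises a separate SAP before unblinding, but a study without blinding has no such event to fix the date.

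**The concern.** The option of 40 and the ceiling of 100 are different kinds of provision. The first rests on a power statement made in advance. The second defines a sufficient number as one that shows a significant effect and then accepts any reason for finding 30 insufficient. A non-significant result at 30 is therefore among the permitted reasons.

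If the team tests at 30, stops when p<0.05 and otherwise recruits more and tests again at 0.05, the null hypothesis gets two or more chances to be rejected. The final p-value then overstates the evidence. A reader of the report could not tell whether N grew for that reason or for a harmless one such as easy recruitment.

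The disagreement between 30, 40 and 100 is a separate fault. It does not itself change type I error, but it leaves unclear which size is the plan.

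**Working it through.** **Inputs.** Two-sided 0.05 without adjustment (8.1). Sizes 30, 40 and 100 (4.1, synopsis, 8.5). Expected improvement 5 T-score points and SD 5, so effect size 1 (synopsis). Paired t-test on change scores. The plan gives no schedule of looks, so the schedules below are assumptions.

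**1. The plan's own power figures.** For a two-sided paired t-test with effect size d, power is P(|T|>t₀.₉₇₅,ₙ₋₁), where T is noncentral t with n−1 degrees of freedom and noncentrality d√n.

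- n=30, d=1: 99.96%, where the synopsis has 86%.
- n=40, d=0.8: 99.85%, where the synopsis has 81%.

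The stated figures do match a one-sided normal-approximation comparison of two equal groups (86.3% with 15 per group, 81.2% with 20 per group), which is not this design. That is a separate error and nothing below depends on it. It does mean that, at the plan's own effect sizes and with its own test, 30 patients already give ample power. A shortage would then have to come from a smaller effect or a larger SD than assumed.

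**2. Type I error when extension depends on the result.** For two looks, the normal approximation gives

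error = 1 − P(|Z₁|<1.96 and |Z₂|<1.96), with correlation √(n₁/n₂).

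- 30 then 40: correlation √(30/40)=0.866, error 0.073.
- 30 then 100: correlation √(30/100)=0.548, error 0.089.

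Simulation with the t-test itself (1,000,000 null trials, rejecting if any look has p<0.05) gives:

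| Looks | Type I error | Equal level per look that restores 5% |
|---|---|---|
| 30 only, or 100 fixed without outcome data | 5.0% | 0.05 |
| 30, 40 | 7.4% | 0.033 |
| 30, 100 | about 9% | 0.027 |
| 30, 40, 100 | 10.8% | 0.022 |

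More frequent looks do worse: 14.9% with a look every 10 patients from 30 to 100, and 19.8% with a look after every patient (400,000 trials each).

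**3. How often extension would be triggered.** This is P(p≥0.05 at n=30) = 1 − power at 30:

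- d=0.2: 81%
- d=0.5: 25%
- d=0.8: 1.2%
- d=1: 0.04%

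**4. Bias in the estimated mean change** (400,000 trials per effect, extending if p≥0.05 at 30):

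| True d | To 40 | To 100 |
|---|---|---|
| 0 | 0.000 SD | 0.000 SD |
| 0.2 | +0.012 | +0.033 |
| 0.3 | +0.017 | +0.046 |
| 0.4 | +0.018 | +0.049 |
| 0.5 | +0.014 | +0.039 |
| 1.0 | +0.0002 | +0.0003 |

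If the plan's SD of 5 is taken as the SD of change, the range over d=0.2 to 0.5 is 0.012×5=0.06 to 0.018×5=0.09 T-score points for 40, and 0.033×5=0.165 to 0.049×5=0.245 points for 100.

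**The case against.** The inflated figures all assume a test at 30 followed by extension on p≥0.05, and no section describes that. The remark about seeing a significant effect can be read as lay wording for expected power, since it directly follows an incomplete power sentence. The two-monthly meeting is a safety and conduct meeting, and its agenda does not say that efficacy results are shown. The study is a pilot that calls its p-values hypothesis-generating and tests many secondary outcomes unadjusted. A single-arm, open-label change from baseline in patients selected for fatigue is also open to regression to the mean and expectation effects, beside which a move from 5% to between 7% and 11% is small. Finally, at the two effect sizes the plan names, 1 and 0.8, extension would almost never be triggered.

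Most of this stands as a limit on the consequence. No look is planned, the bias is small, and the hypothesis-generating label lowers the stakes. It does not remove the point. Section 8.5 states a permission that is not limited to design-stage power, section 8.4 excludes only a formal interim analysis, and no other section closes the gap. Section 8.1 still commits to reporting p-values at 0.05, and the label cannot make a p-value interpretable when the rule that fixed N is unknown. The route matters when the true effect is null or modest, and that is where the error rate matters most.

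**Conclusion.** The concern holds. The plan does not guarantee its 0.05 level, because it allows N to rise from 30 to as many as 100 without excluding outcome data from the decision. The error stays at 5% if the increase ignores outcomes. Under the assumed schedules with up to three looks it is between about 7.4% and 10.8% if the increase follows a non-significant test at 30, and higher with more looks. The effect on the estimate is minor: at most about 0.05 SD, zero under the null and below 0.001 SD at effect size 1.

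The conflict between 30, 40 and 100 is a separate inconsistency that also needs resolving. Given the pilot status and the conditional harm, this should be corrected but does not undermine the study.

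**What to change.** - State one target N and one maximum N, identical in the synopsis, section 4.1 and section 8.5.
- In 8.5, replace the open-ended ground for enlargement with a statement that any increase is decided without summarising PROMIS-Fatigue change or any other efficacy data, for example on recruitment or resource grounds. Name who decides, and report when and why N changed.
- In 8.4, state that efficacy results are not reviewed, including at the two-monthly meetings, until enrolment closes.
- Keep the section 8.1 analysis set (everyone with at least one day of use).

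This is wording only and needs no extra patients. The sponsor gives up the freedom to extend after a non-significant result.

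If an outcome-based extension is wanted instead, declare the looks in 8.4 and use an adjusted level at each: about 0.033 for 30/40, 0.027 for 30/100, or 0.022 for 30/40/100. For the two-look schedules, the effect detectable with 80% power at the 30-patient look rises from 0.53 SD to 0.56 SD (30/40) or 0.58 SD (30/100). Power at that look for an effect of 0.5 SD falls from 75% to 69% or 66%.
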